## **6.2 Preexisting Condition**

A preexisting condition is one that is present at the start of the study. A preexisting condition should be recorded as an adverse event if the frequency, intensity, or the character of the condition worsens during the study period.

At screening, any clinically significant abnormality should be recorded as a preexisting condition. At the end of the study, any new clinically significant findings/abnormalities that meet the definition of an adverse event must also be recorded and documented as an adverse event.

## **6.3 Post-study Adverse Event**

All unresolved AEs will be followed by the study team until the events are resolved, the subject is lost to follow-up, or the AE is otherwise explained. A review of AEs which the subject or subject's physician believe might reasonably be related to participation in the study will be performed up to 12 months following treatment.

## **6.4 Hospitalization, Prolonged Hospitalization or Surgery**

Any AE related to the study intervention that results in hospitalization or surgery should be documented and reported as a serious AE.

Neither the condition, hospitalization, prolonged hospitalization, nor surgery are reported as an adverse event in the following circumstances:

- Hospitalization or prolonged hospitalization for diagnostic or elective surgical procedures for a preexisting condition. Surgery should not be reported as an outcome of an adverse event if the purpose of the surgery was elective or diagnostic and the outcome was uneventful.

## **6.5 Recording of Adverse Events**

The study team will seek information on adverse events by specific questioning between baseline and the follow-up visits. Information on all adverse events will be recorded immediately in the adverse event section of the specific questionnaire as well as in an adverse event form.

All adverse events occurring during the study period will be recorded. The clinical course will be followed until resolution, stabilization, or until it has been ultimately determined that the study treatment or participation is not the probable cause. Serious adverse events that are still ongoing at the end of the study period will be followed up, to determine the final outcome. Any serious adverse event that occurs after the study period and is considered to be at least possibly related to the study treatment or study participation will be recorded and reported immediately.

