### 1.2 Investigational Treatments

The current study would randomize men 1:3 into one of two treatment cohorts: 1. Observation followed by CCH or 2. CCH followed by observation. This study design offers the benefits of a randomized,

controlled trial (highest level of evidence), while also providing data for a second set of publications evaluating the cross-over to treatment phase (for controls). RCTs are particularly important in PD, where the disease changes over time in a percentage of men as a function of its natural history. This would also allow blinding of measurements using photographs (single-blinded assessments), which provides further study rigor. See Figure 1 for overall study schema.

1. No treatment (control) followed by CCH. Men in this cohort would undergo baseline assessments followed by no treatment for 6 months and then repeat assessments. Men would then cross-over to CCH treatment and undergo up to 8 injections (or until curvature is <15 degrees). Interval assessments would be performed with the 1st injection of each series, and final assessments would then be performed 6 weeks following the final injection.
2. CCH followed by no treatment. Men in this cohort would undergo baseline assessments followed by up to 8 injections of CCH (or until curvature is <15 degrees). Interval assessments would be performed with the 1st injection of each series and 6 weeks following completion of treatment. Men then would not undergo any additional treatments for 6 months, after which final assessments would then be performed.

During CCH administration, several key differences from the IMPRESS protocols would be performed. Please note that each of these changes have been slowly implemented in the investigators' practice over time to improve overall efficacy of therapy:

	IMPRESS Protocol	Current Study Protocol
Amount administered	0.58 mg	0.9 mg
Suspension volume	0.37 ml	0.7 ml
Method of injection	Into plaque	To point of maximal curvature in the tunica, as determined with an erection at the first injection of each series
Administration schedule	1-3 days apart	1 day apart
Mechanical device traction	None	RestoreX 30-60 min daily until 6 weeks after final injection
Office modeling	Performed 1-3 days after initial injections (defined as "firm")	10-15 lbs of force performed at the time of 2 nd injection

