Home modeling	3x daily modeling performed, gentle attempts at straightening erection	10-15 lbs of force performed at least one daily; straightening during erection
Penile wrapping	No comments	Mandatory x 5 days after 2 nd injection of each series

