### **2.2 Secondary Outcomes**

1. Compare IIEF outcomes between control and treatment groups at 6 months
2. Compare penile curvature changes in control men at baseline and 12 months (i.e. prior to and following cross-over to CCH)
3. Compare penile length changes in control men at baseline and 12 months (i.e. prior to and following cross-over to CCH)
4. Compare PDQ changes in control men at baseline and 12 months (i.e. prior to and following cross-over to CCH)
5. Compare IIEF changes in control men at baseline and 12 months (i.e. prior to and following cross-over to CCH)
6. Compare penile length changes between control and treatment groups at 6 months
7. Report adverse events at 6 and 12-month time points

8. Report changes in penile curvature between 6 and 12-month assessments for CCH men

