### 3.5 Study Schema

Patients meeting criteria who have consented will be randomized to either control or CCH x 6 months, followed by a cross-over phase where controls will receive CCH. See Figure 1 for full study schema.

1. Control. Men in this cohort would undergo baseline assessments followed by no treatment for 6 months and then repeat assessments. Men would then cross-over to the CCH treatment phase and undergo up to 8 injections (or until curvature is <15 degrees, whichever comes first). Final assessments would then be performed 6 weeks following the final injection.
2. CCH followed by observation. Men in this cohort would undergo baseline assessments followed by up to 8 injections of CCH (or until curvature is <15 degrees). Assessments would then be performed 6 weeks after completion of treatment. Men then would not undergo any additional treatments for 6 months, after which they would have final assessments performed.

The following table provides an overview of the objective and subjective questionnaire administration:

	Baseline	1 st CCH of each series	6-weeks after CCH completed	End of no treatment phase
Baseline disease specific questionnaire	X			
Baseline subjective questionnaire	X			
IIEF	X	X	X	X
PDQ	X	X	X	X
1 st injection Xiaflex questionnaire		X	X	

Post Xiaflex subjective questionnaire			X	
Post no treatment subjective questionnaire				X
Length measurement	X	X	X	X
Curve measurement	X	X	X	X
Penile ultrasound	X			

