### **5.2 Statistical Analysis**

The current study is considered exploratory in nature. Analyses will be performed using comparisons within and between patient cohorts. All captured data will be utilized as a point of comparison based on accepted standards (e.g. IIEF subdomains, PDQ subdomains, etc.). All data will be analyzed to determine if it is normative / non-normative and will be described and compared appropriately (mean, SD versus median, IQR).

Patients with partial missing data will have all available data included for analysis, with no attempts made to statistically replace missing variables. All data will be analyzed using an intent-to-treat analysis.

Adverse events will be reported as a total as well as compared between cohorts.

A power analysis was performed using historical data from another one of the investigators' RCTs to determine the standard deviation for control men between two sequential assessments. Results of absolute curvature improvements demonstrated a standard deviation of 16 degrees or 27% relative improvement. Using a 0.05 alpha threshold, power of 80%, and expected cohort size of 30 (assuming 30 with 6-month data) this would allow us to distinguish differences over 17 degrees or 29%. Given the investigators' current improvements of 60% with the investigators' preliminary data, we would expect this study to have sufficient power to demonstrate a clinically and statistically significant finding.

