## 6 Safety and Adverse Events

### Definition of Adverse Event

Unanticipated Problems Involving Risk to Subjects or Others (UPIRTSO) - any unanticipated problem or adverse event that meets the following three criteria:

Serious: Serious problems or events that results in significant harm, (which may be physical, psychological, financial, social, economic, or legal) or increased risk for the subject or others (including individuals who are not research subjects). These include: (1) death; (2) life threatening adverse experience; (3) hospitalization - inpatient, new, or prolonged; (4) disability/incapacity - persistent or significant; (5) breach of confidentiality and (6) other problems, events, or new information (i.e. publications, interim findings, product labeling change) that in the opinion of the local investigator may adversely affect the rights, safety, or welfare of the subjects or others, or substantially compromise the research data, AND

Unanticipated: (i.e. unexpected) problems or events are those that are not already described as potential risks in the protocol, consent document, or not part of an underlying disease. A problem or event is "unanticipated" when it was unforeseeable at the time of its occurrence. A problem or event is "unanticipated" when it occurs at an increased frequency or at an increased severity than expected, AND

Related: A problem or event is "related" if it is possibly related to the research procedures.

Adverse Event - an untoward or undesirable experience associated with the use of a medical product (i.e. drug, device, biologic) in a patient or research subject.

Serious Adverse Event - adverse events are classified as serious or non-serious. Serious problems/events can be well defined and include:

- Death
- Life threatening adverse experience
- Hospitalization
- Inpatient, new, or prolonged; disability/incapacity
- And/or per protocol may be problems/events that in the opinion of the sponsor-investigator may have adversely affected the rights, safety, or welfare of the subjects or others, or substantially compromised the research data.

All AEs that do not meet any of the criteria for serious, should be regarded as non-serious AEs.

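### Adverse events are to be compared between cohorts, but control men are questioned less often and the AE definition and window are anchored to treatment, so background events in controls are likely to be under-counted

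*Combined protocol and SAP*

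**What the plan says.** **The comparison.** Section 5.2: "Adverse events will be reported as a total as well as compared between cohorts". Section 2.2 lists as a secondary outcome: "Report adverse events at 6 and 12-month time points". No denominator, exposure time or ascertainment rule is given.

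**How events are found.** Section 6.5: "The study team will seek information on adverse events by specific questioning between baseline and the follow-up visits". The same section says that every AE in the study period is recorded. Section 4.2 lists an AE form completed by staff, and sends the reader to the table in 3.5 for the timing of questionnaires. That table has no AE row.

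**Visits.** For controls, 3.5 says: "Men in this cohort would undergo baseline assessments followed by no treatment for 6 months and then repeat assessments". The CCH arm has up to 8 injections, fewer if curvature falls below 15 degrees. Section 1.2 places its interval assessments at the first "injection of each series and 6 weeks following completion of treatment".

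**Definition and window.** Section 6 defines an AE as "an untoward or undesirable experience associated with the use of a medical product (i.e. drug, device, biologic) in a patient or research subject". Section 6.1 sets the follow-up period at 6 weeks from the last study treatment. Section 6.2 counts any worsening of a preexisting condition, without reference to a product.

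**The concern.** Section 1.2 justifies randomisation by the changing natural history of the disease. The untreated controls are therefore the reference for symptoms that would have occurred anyway. If they are asked once about 6 months, while CCH men are asked every time a series starts, minor or passing events are more likely to be forgotten in the control arm. A definition and a window written around treatment add to this: staff who apply section 6 and 6.1 could leave out a control man's new symptom that staff who apply 6.2 and 6.5 would record.

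At stake is the meaning of the AE comparison for background and disease-related events. A difference produced by unequal questioning would look like a treatment effect, and it could not be repaired once the data are in.

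**Working it through.** The plan states no AE rate, visit total or AE sample size, so there is no figure of its own to reproduce.

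**1. Visit count, baseline to the end of the randomised phase.** The table in 1.2 refers to a first and a second injection in each series, so I infer 2 per series. A full course is then 8 / 2 = 4 series. Scheduled assessments = series + 1 (the 6-week visit). Clinic contacts = 2 × series + 1. If the first injection falls on the baseline day, subtract one from each to get post-baseline counts (in brackets).

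| Course | Scheduled assessments | Clinic contacts |
|---|---|---|
| Control | 1 | 1 |
| CCH, stops after 1 series | 2 (1) | 3 (2) |
| CCH, 2 series | 3 (2) | 5 (4) |
| CCH, 3 series | 4 (3) | 7 (6) |
| CCH, 4 series | 5 (4) | 9 (8) |

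For a full course the contrast is 1 against 4–5 assessments, or 1 against 8–9 contacts. Second-injection days come 1 day after the first and shorten recall very little, so 4–5 is the more relevant count.

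**2. Definition and window side by side.** Section 6 requires an association with a medical product; 6.2 and 6.5 do not. The period in 6.1 starts from the last study treatment, and a control man has none before cross-over. No section says which text governs the no-treatment phase.

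**3. Illustration of the recall effect (assumptions, not document figures).** Suppose that background events occur at the same rate in both arms, uniformly over 26 weeks; that k visits are evenly spaced, with gap L = 26/k weeks; and that an event is reported at the next visit with probability 2^(−lag/h), where h is a recall half-life. The proportion captured is

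C(k, h) = [h / (L ln 2)] × [1 − 2^(−L/h)].

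For example, with h = 13 and k = 1: [13 / (26 × 0.693)] × (1 − 0.25) = 0.54.

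| h (weeks) | k = 1 | k = 4 | k = 5 | k = 8 | Ratio to k = 1 (4 / 5 / 8 visits) |
|---|---|---|---|---|---|
| 4 | 22% | 60% | 66% | 76% | 2.73 / 3.00 / 3.48 |
| 13 | 54% | 85% | 87% | 92% | 1.56 / 1.61 / 1.70 |
| 52 | 85% | 96% | 97% | 98% | 1.13 / 1.14 / 1.16 |

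With no true difference, the apparent CCH:control ratio runs from about 1.1 to 3.5. It depends far more on recall than on whether 5 or 8 visits are counted.

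**4. Denominators.** At 1:3 with 40 men the arms hold 10 and 30. Equal rates per man would give 30 / 10 = 3 times as many events in the CCH arm, so raw totals cannot be compared.

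**The case against.** The strongest case against is that the plan may already capture control events adequately. Section 6.5 records all AEs in the study period, 6.2 covers worsening of existing conditions, and alprostadil at curvature assessments (4.2) means that controls also receive a drug. The phrase in 6.5 about questioning between baseline and the visits could mean that one interview covers the whole interval. The questionnaires, which may include AE questions for the end of the no-treatment phase, are not in the text available. The outcome is secondary, the study is declared exploratory, and about 10 controls give an imprecise comparison whatever is done.

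Much of this stands, and it rules out several stronger readings:

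- A reader might infer from section 6 that almost no control event could count. Sections 6.2 and 6.5 and the use of alprostadil do not support that; the texts conflict, which is a different problem.
- A reader might take 8 contacts against 1 as the typical contrast. It is a full-course maximum that counts second-injection days, and 6.5 does not say that questioning takes place on those days.
- A reader might conclude that the comparison cannot separate treatment effects from disease at all. Erectile function and curvature are measured in both arms by IIEF and curve assessment, whatever a man recalls, and injection-specific events are little affected.

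The objection does not remove the unequal look-back. Even one thorough interview asks controls to recall 6 months, and nothing in the plan sets equal intervals.

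**Conclusion.** The point holds as a likely bias, not a demonstrated one. As written, the plan questions the arms at unequal intervals and anchors the AE definition and window to treatment, in conflict with 6.2 and 6.5. The probable direction is under-counting of background events in controls, and so an overstated CCH excess for minor or disease-related events.

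The size is unknown. The range of 1.1 to 3.5 rests on the assumed half-lives, evenly spaced visits and equal true rates; a reader should not treat any single false risk ratio as established. The visit counts rest on 2 injections per series and a full course; with early stopping after one series the assessment contrast can shrink to 1 against 1–2. The primary endpoints are not affected. The change is still worth making before enrolment, because it is cheap and lost recall cannot be recovered.

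**What to change.** 1. In section 6, define an AE as any untoward occurrence from enrolment, whether or not a product was used, and record relatedness separately; the form in 6.6.1 already has that field. Reconcile sections 6, 6.1, 6.2 and 6.5, and state a reporting window for the no-treatment phase.
2. Add an AE row to the 3.5 table. Ask both arms the same AE questions at the same fixed calendar intervals from randomisation, by phone or email for controls. Calendar intervals are needed because the documents give no spacing between series to which control contacts could be matched.
3. In 5.2, compare per-patient proportions or person-time rates instead of raw totals.

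If no contacts are added, limit the between-cohort comparison to events elicited by the same questions at the end-of-phase visit with the same look-back period, and report injection-visit events descriptively. The limitation is that a short look-back leaves out earlier events in both arms.

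Cost: wording changes, and a few short contacts per control by the existing coordinator. Three each would be 3 × 10 = 30. CCH men would need an extra contact only where no visit falls near the calendar point. The comparison stays imprecise: with about 10 controls, one man is 10 percentage points.

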## **6.6 Reporting of Serious Adverse Events and Unanticipated Problems**

When an adverse event has been identified, the study team will take appropriate action necessary to protect the study participant and then complete the Adverse Event Form. The sponsor-investigator will evaluate the event and determine the necessary follow-up and reporting required.

### **6.6.1 Sponsor-investigator Reporting: Notifying the Western IRB**

An adverse event form will be completed for any serious adverse event. This will be reported to the Western IRB in a de-identified manner.

The study team will report to the Western IRB any UPIRTSOs and Non-UPIRTSOs.

Information collected on the adverse event form (and entered into the research database)

- Subject's ID
- Description of adverse event
- The date the adverse event occurred and resolved (if applicable)
- Intensity
- Outcome
- Action taken to address
- Relationship to study
- Impact on study withdrawal
- Classification as serious or not

The sponsor-investigator will review all adverse event reports to determine if specific reports need to be made to the IRB. The sponsor-investigator will sign and date the adverse event report when it is reviewed. For this protocol, only directly related SAEs/UIRTSOs will be reported to the IRB.

### **6.6.2 Stopping Rules**

Any serious adverse event which is determined to reasonably be related to the study treatment by the sponsor-investigator will result in immediate discontinuation of the therapy. If 5 patients develop serious adverse events, the study will be halted with re-review required by the Western IRB prior to consideration of study resumption.

### **6.6.3 Medical Monitoring**

Medical monitoring of serious adverse events will be performed by the study investigator on a monthly-basis if serious adverse events have been reported.

## **7 Data Handling and Record Keeping**

### **7.1 Confidentiality**

Information about study subjects will be kept confidential and managed according to the requirements of the Health Insurance Portability and Accountability Act of 1996 (HIPAA). Those regulations require a signed subject authorization informing the subject of the following:

- What protected health information (PHI) will be collected from subjects in this study
- Who will have access to that information and why
- Who will use or disclose that information
- The rights of a research subject to revoke their authorization for use of their PHI.

In the event that a subject revokes authorization to collect or use PHI, the investigator, by regulation, retains the ability to use all information collected prior to the revocation of subject authorization. For subjects that have revoked authorization to collect or use PHI, attempts should be made to obtain permission to collect at least vital status (long term survival status that the subject is alive) at the end of their scheduled study period.

### **7.2 Source Documents**

Source data comprise all information, original records of clinical findings, observations, or other activities in a clinical trial necessary for the reconstruction and evaluation of the trial. Source data are contained in source documents. Examples of these original documents, and data records include: hospital records, clinical and office charts, laboratory notes, memoranda, subjects' diaries or evaluation checklists, pharmacy dispensing records, recorded data from automated instruments, copies or transcriptions certified after verification as being accurate and complete, microfiches, photographic negatives, microfilm or magnetic media, x-rays, subject files, and records kept at the pharmacy, at the laboratories, and at medico-technical departments involved in the clinical trial. When applicable, information recorded on the CRF shall match the Source Data recorded on the Source Documents.

### **7.3 Records Retention**

The sponsor-investigator will maintain records and essential documents related to the conduct of the study. These will include subject case histories and regulatory documents.

The sponsor-investigator will retain the specified records and reports during the study and for a period of 2 years after the investigation is terminated or completed.

